4.0 DRUG/DEVICE INFORMATION

The following devices will be utilized in this pilot study:

- 1. MRI: The MRI scanning procedure requires that the participants be confined in a small, partially enclosed space. The sound of the MRI scanner can be loud, but will be reduced by special ear plugs. The tasks may be boring or difficult. In addition, the magnetism of the machine attracts certain metals; therefore, people with these metals in them (specifically pacemakers, infusion pumps, aneurysm clips, metal prostheses, joints, rods, or plates) will be excluded from the study. The "metal" in dental fillings is less susceptible to magnetism and is therefore allowed. There are no known adverse effects resulting from exposure to the MRI scan. There are no other known risks when the scanner is operated within its nominal range as discussed above. The FDA Center for Devices and Radiological Health, released the document "Criteria for Significant Risk Investigations of Magnetic Resonance Diagnostic Devices" on July 15, 2003. This describes their current evaluation of risk related to MRI. Notably, both software and hardware features of the instrument prevent this software from executing commands outside of a well-defined range defined as safe by the FDA.
- 2. Quantitative EEG: TruScan 32 EEG Acquisition System (Deymed Diagnostics, Payette, ID), including EEG cap, EEG amplifier and EEG adapter, will be used in the study.
- 3. Quotient system: Quotient® (formerly known as MMAT, the McLean Motion and Attention Test) is a non-invasive device providing objective measures of an individual's ability to inhibit motor activity, sustain attention and suppress impulsive response. Quotient uses motion tracking technology to track an individual's micromovements while he or she completes a 15-20 minute computerized test. After the test is completed, patterns of motion, accuracy of the responses, and fluctuations in attention state will be analyzed and scored using proprietary algorithms. Quotient is cleared by the FDA with the intended use to provide objective measures of hyperactivity, impulsivity and inattention to aid in the clinical assessment of ADHD.
- 4. SMARTfitTM Mini 9 On-Frame: The SMARTfitTM Mini 9 On-Frame is a vertical frame-mounted 9 target 46" x 46" Panel with CPU controller, timeclock, score display, sound system and 4 tracks of themable voice/tones/music. The SMARTfitTM Mini 9 On-Frame can capture the accuracy and movement time, which serve as performance feedback to participants.

5.0 SELECTION AND WITHDRAWAL OF SUBJECTS

- 5.1 Inclusion Criteria:
 - 1) 50-85 years of age
 - 2) Diagnosis of idiopathic Parkinson's disease using the UK Brain Bank criteria (as determined by the study movement disorders neurologist) with Hoehn and Yahr stage 1-2
 - 3) No contraindications to exercise including untreated cardiovascular disease or stroke
 - 4) Medically stable and optimized on their medications
 - 5) Able to ambulate independently with or without device
 - 6) No other neurologic, neuromuscular, or orthopedic disease
 - 7) No serious cognitive deficits and able to participate in the informed consent process
 - 8) With medical clearance from primary care physician to participate in the physical therapy intervention
 - 9) No contraindications for MRI
- 5.2 Exclusion Criteria

Participants will be excluded from participation if they have:

- 1) Severe cardiac disease (New York Heart Association classification II-IV)
- 2) Systolic blood pressure reduction of greater than 20 mmHg with standing
- 3) A history of poorly controlled or brittle diabetes
- 4) A history of lower limb amputation

- 5) Been prescribed any new dopamine replacement medications or new mood stabilizer medications.
- 6) Presence of a lower limb non-healing ulcer
- 7) Montreal cognitive assessment score of less than 21
- 8) The presence of any medical condition which the investigator believes might present an unacceptable health risk to the subject should they participate in the study
- 9) Electrically, magnetically, or mechanically activated implant (such as cardiac pacemakers or intracerebral vascular clip)
- 10) Metal in any part of the body including metal injury to the eye
- 11) History of brain lesions (such as stroke), seizures, or unexplained spells of loss of consciousness
- 12) Pregnant or breast-feeding
- 13) With other neurologic, neuromuscular, or orthopedic disease that would interfere with ability to participate in exercise training
- 14) Currently participating in other studies

Cardiac Tolerance

Cardiac conditions that would cause exclusion from the study include (but are not limited to) unstable angina within last 3 months, myocardial infarction within last 3 months, serious cardiac dysrhythmia, right main coronary artery disease, aortic stenosis, currently decompensated heart failure of pulmonary edema, severe system hypertension (SBP > 180 or DBP > 110), fixed-rate artificial pacemaker, hypertrophic cardiomyopathy, pulmonary embolus or infarction within the last 6 months. Each participant's cardiac status will be verified with his/her physician.

Blood Pressure/Heart Rate at rest and with exercise³³

Resting: Participants in the study must have a resting SBP<180 and DBP<110. Heart rate must be <100 at rest and systolic blood pressure must not drop > 20 with standing. **Exercise:** Participants in the study must have a SBP<200 and DBP<110 when measured after 2 minutes rest from exercise.

Participants whose heart rate or blood pressure is greater than the values stated above will be excluded from the study.

5.3 Withdrawal Criteria

Participants will have the option to withdraw from this study at any time. Withdrawal from this study will not affect their participation in any other study within the USC Neurorestoration center. The investigators may also choose to terminate a participant from this study, if he or she suffers a severe adverse event, does not follow study requirements, or investigators feel that continued participation will put the participant at a greater risk than indicated.

6.0 STRATIFICATION/DESCRIPTIVE FACTORS/RANDOMIZATION SCHEME

Participants will be assigned to receive the SMARTfit training or conventional physical training first with stratified randomization. Specifically, Hoehn and Yahr stage I and II will be used as the two strata. Randomization will be performed within each Hoehn and Yahr stage (I and II) using sealed envelopes with a 1:1 allocation ratio between the two training orders. The number of participants with Hoehn and Yahr stage I and II will be evenly assigned to the two training orders to ensure equivalent disease severity.

7.0 STUDY AGENT ADMINISTRATION OR INTERVENTION AND TOXICITY MANAGEMENT PLAN

For training protocol, see section 3.1 at page 7. Training will be discontinued if participants continue experiencing a RPE above 8 or show signs of cardiac intolerance (shortness of breath, leg cramps, agina, lightheadness, confusion, nausea, blood pressure above guidelines lists in Section 5.2). Individuals whose symptoms resolve after training is discontinued will be invited to participate in the next training session (48 hours later). If these symptoms occur a second time, individuals will be removed from the study and will be encouraged to see a physician as soon as possible.

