- c. Any time rate of change of gradient fields (dB/dt) sufficient to produce severe discomfort or painful nerve stimulation.
- d. A-weighted root mean square (rms) sound pressure level greater than 99 dBA with hearing protection in place.

Under no circumstances will our instrument be operated outside of these non-significant ranges on human subjects. The small risk of metal objects being dislodged will be reduced by the screening process previously described. Headphones and ear protectors will be used to reduce any discomfort that might be associated with the scanner noise. The use of headphones and video systems will minimize the potential discomfort of claustrophobia.

Protection against MRI risk

The 3T Prisma whole-body MRI systems installed at the Center of Image Acquisition (CIA), Stevens Neuroimaging and Informatics Institute located at HSC, which offers state-of-the-art imaging platforms to characterize TMS induced physiological, metabolic and functional changes of human brain.

The participants will be screened for appropriateness for study participation using the inclusion and exclusion criteria. In addition, participants will be introduced to exercise activities and monitored by a trained Physical Therapist (PT) at each visit. The PT will keep documentation records for each treatment session that will monitor 1) the subjects cardiovascular exercise tolerance through vital sign assessment and 2) any signs of musculoskeletal adverse response. The PT will be instructed to contact the PI immediately if an adverse response that requires medical intervention occurs. Participants will practice

the activities with the PT in the clinical setting and will receive feedback to ensure proper form and safety during each session. In addition, subjects will be notified that they can call the PI at any time if any adverse effects occur.

Ongoing monitoring of risks and benefits will occur by a monthly site visit by the PI who will review all documentation. The PI will determine the balance between risks and benefits and will notify the IRB if a change in the intervention protocol in order to minimize risk is required. In the case of an actual adverse event, the PI will complete the "IRB Report of an Internal Adverse Event" form and report the event to the IRB within 5 days of the event.

8.2 Dosage change based on toxicity.

Not applicable. No modification of medication will be included.

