8.3 Adverse Event Reporting

All adverse events will be reported to the IRB on the USC Health Sciences Campus. Any unexpected, severe, or fatal adverse events will be reported to the IRB within 24 hours. Minor adverse events will be summarized and included in the annual continuation review and final report.

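### After a first episode of angina or confusion that resolves, Section 7.0 allows return to training at the next session with no required investigator or physician review

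*Combined protocol and SAP*

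**What the plan says.** Section 7.0 stops training for persistent perceived exertion above 8, or for participants who "show signs of cardiac intolerance (shortness of breath, leg cramps, agina, lightheadness, confusion, nausea, blood pressure above guidelines lists in Section 5.2". The third item is read here as angina. All the listed signs share one rule. After a first episode: "Individuals whose symptoms resolve after training is discontinued will be invited to participate in the next training session (48 hours later". After a second: "If these symptoms occur a second time, individuals will be removed from the study and will be encouraged to see a physician".

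Section 8.1 has participants "monitored by a trained Physical Therapist (PT) at each visit", and sets the therapist's duty to escalate: "The PT will be instructed to contact the PI immediately if an adverse response that requires medical intervention occurs". For an actual adverse event the PI must complete a form and "report the event to the IRB within 5 days of the event". Section 8.3 adds: "Any unexpected, severe, or fatal adverse events will be reported to the IRB within 24 hours". It also says: "Minor adverse events will be summarized and included in the annual continuation review and final report".

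Section 5.2 sets a post-exercise limit of SBP below 200 and DBP below 110, measured after 2 minutes of rest. It says that participants above its blood pressure or heart rate values are excluded from the study.

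**The concern.** Angina and confusion receive the same handling as leg cramps and nausea. If the episode settles when exercise stops, nothing in Section 7.0 requires anyone with medical responsibility to consider it before the next session.

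The protocol's own text shows why this matters. Participants are aged 50 to 85 (Section 5.1), Section 8.1 names heart attack and stroke among the exercise risks, and sessions aim for perceived exertion of 6 to 8 (Section 3.1). Section 5.1 requires that there be no untreated cardiovascular disease, and Section 5.2 excludes unstable angina within 3 months and a history of stroke. Whether a first episode in training means that a participant no longer meets those standards is a medical question. As written, the participant can be training again two days later without anyone being required to answer it.

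**Working it through.** No sample size, power or event figure bears on this point, so the check is a comparison of text. The question put to each provision is whether it makes PI or physician review a condition of return after a first episode that resolves.

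- **Section 7.0, first episode.** Condition: symptoms resolve after stopping. Return: next session, 48 hours later. Review required: none.
- **Section 7.0, second episode.** The participant is removed and encouraged to see a physician. This comes after the return in question.
- **Sections 3.1, 5.1 and 5.2, physician approval, medical clearance and verification of cardiac status.** These are stated with recruitment and eligibility. Nothing says they are renewed after an episode.
- **Section 3.1, scaling of difficulty.** Required when perceived exertion exceeds 8. An episode of angina at a rating within the 6 to 8 target does not trigger it, and it is not a review.
- **Section 8.1, therapist to PI.** Immediate contact is required when the response needs medical intervention. An episode that settles on stopping need not meet that test.
- **Section 8.1, PI review of documentation.** Monthly, so it will often fall after a 48-hour return, and it is not tied to return.
- **Sections 8.1 and 8.3, IRB reporting.** Within 5 days (5 × 24 = 120 hours) for an actual adverse event, within 24 hours if unexpected, severe or fatal, and at annual review for minor events. The 24-hour report falls before the 48-hour return and the 5-day limit after it. Neither is a clearance to resume.
- **Section 5.3, termination by investigators.** Discretionary.
- **Section 8.4, data monitoring committee.** Not applicable in this trial.

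No provision supplies the condition.

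On blood pressure, two texts use the same limits. Section 5.2 attaches exclusion from the study to a value above them. Section 7.0 treats a value above them as a sign that stops training, then allows return after a first episode and removes at a second. Whether these conflict depends on two matters the text leaves open: whether Section 5.2 governs people already in training or only entry, and whether a reading that falls back counts as symptoms that resolve.

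**The case against.** The PI is not absent. The PI completes the report for an adverse event, must be called if medical intervention is needed, reviews documentation monthly, can be telephoned by participants, and may terminate on grounds of risk. An episode classed as unexpected or severe must be reported within 24 hours, before the return. A therapist takes vital signs, and sessions are monitored one to one by staff certified in CPR and first aid. An invitation does not compel anyone to return. All of this stands and reduces the exposure. A reader might infer that an episode would go unnoticed or that no investigator could intervene, and the documents do not support that. What remains is narrower: none of these provisions makes review a condition of return.

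A reader might also infer that Sections 5.2 and 7.0 flatly contradict each other on blood pressure. The documents do not establish this. The limit sits under exclusion criteria, and entry limits in 5.2 with in-training handling in 7.0 is a coherent reading. The wording about participants in the study, measured after exercise, gives some support to the on-study reading. The absence of an exercise test from the Section 9.0 calendar adds little, because the calendar also omits resting blood pressure, Hoehn and Yahr staging and physician clearance. What stands is an ambiguity, and it does not justify permanent removal after one reading.

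Finally, a reader might take the interval from return to the 5-day IRB limit (120 − 48 = 72 hours) as a measure of risk. It is not one, because IRB reporting does not control return.

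**Conclusion.** The concern holds in a limited form. Section 7.0 states a return rule for signs that include angina and confusion, and neither that rule nor any other section requires PI or physician review before training resumes after a first episode. This rests on the text alone, with the protocol's spelling read as angina. No magnitude is claimed: the documents give no event rate, and at most 12 people are to be enrolled. Singling out angina and confusion from the other listed signs is a clinical judgement; the protocol itself does not rank them.

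The blood pressure point is secondary. Two readings are open, staff could reach different outcomes from the same measurement, and the protocol should say which applies. The change is worth making because it is cheap and concerns participant safety. It does not affect the statistical analysis in Section 13.0.

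**What to change.** In Section 7.0, after a first episode of angina or confusion: pause training, notify the PI the same day, and require documented clearance from the participant's physician before return. Keep removal from the study at a second episode.

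Also in Section 7.0, state which rule applies during training when blood pressure exceeds the Section 5.2 post-exercise limit, and whether a reading that falls back counts as resolved. This should not presume permanent removal after a single reading: that would be a new restriction if 5.2 governs entry only, and would be stricter than the rule proposed here for angina.

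The cost is protocol wording plus one contact per episode with a physician whom Section 3.1 already has the study contact for every participant. Waiting for clearance may delay a few of the 24 sessions in an 8-week programme.

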8.0 ASSESSMENT OF EFFICACY AND SAFETY

8.1 Side effects/Toxicities to be monitored.

The risks to participants associated with this study include the time needed to complete the physical therapy sessions and the potential for muscle soreness, strains, or sprains that is a natural part of participating in a training program.

The overall risk classification is greater than minimal risk but less than significant risks.

Potential Risks of Exercise

There are minimal risks associated with participation in exercise and physical training. These risks include muscle strains and/or sprains and muscle soreness, in addition to cardiovascular events such as heart attack and stroke. Physical training in this proposed study is considered safe and effective for improving motor performance in PD. To minimize these risks, all sessions will be monitored by research personnel that are CPR/First Aid certified. Additionally, the participant to researcher (1:1) ratio will be low so that research personnel can provide adequate attention to participants during training.

Potential Risks of EEG

The use of EEG is largely low risk although placement of disks may cause slight scalp irritation in that the discs must be placed directly on the scalp. To prevent more than minimal discomfort we will be in constant communication with the participants on how the placement of the EEG cap feels and will modify placement based on reported comfort level. If the cap becomes too uncomfortable for the participant to bear then the cap will be removed and the participant is free to discontinue participation in the study.

The gel used to put the EEG discs on the head is sometimes sticky and the discs may scratch the outer layer of scalp skin. Investigators will take care to try to minimize scratching the scalp skin during application.

Potential Risks of blood sample collection

There are minimal risks associated with blood sample collection. There is a small risk of bruising and fainting, and a rare risk of infection.

Summary of MRI risks

The FDA considers MRI devices to be of non-significant risk if they meet the following criteria (we summarize only the relevant portions of this document):

- a. Field strength less than 8 Tesla
- b. RF power deposition (measured as the specific absorption rate or SAR) to the patient is limited by law, and by the instrument, to less than 3 W/kg in the head. Notably, human imaging with SAR of double that has been demonstrated to be safe in normal subjects³⁴.
- c. Any time rate of change of gradient fields (dB/dt) sufficient to produce severe discomfort or painful nerve stimulation.
- d. A-weighted root mean square (rms) sound pressure level greater than 99 dBA with hearing protection in place.

Under no circumstances will our instrument be operated outside of these non-significant ranges on human subjects. The small risk of metal objects being dislodged will be reduced by the screening process previously described. Headphones and ear protectors will be used to reduce any discomfort that might be associated with the scanner noise. The use of headphones and video systems will minimize the potential discomfort of claustrophobia.

Protection against MRI risk

The 3T Prisma whole-body MRI systems installed at the Center of Image Acquisition (CIA), Stevens Neuroimaging and Informatics Institute located at HSC, which offers state-of-the-art imaging platforms to characterize TMS induced physiological, metabolic and functional changes of human brain.

The participants will be screened for appropriateness for study participation using the inclusion and exclusion criteria. In addition, participants will be introduced to exercise activities and monitored by a trained Physical Therapist (PT) at each visit. The PT will keep documentation records for each treatment session that will monitor 1) the subjects cardiovascular exercise tolerance through vital sign assessment and 2) any signs of musculoskeletal adverse response. The PT will be instructed to contact the PI immediately if an adverse response that requires medical intervention occurs. Participants will practice

the activities with the PT in the clinical setting and will receive feedback to ensure proper form and safety during each session. In addition, subjects will be notified that they can call the PI at any time if any adverse effects occur.

Ongoing monitoring of risks and benefits will occur by a monthly site visit by the PI who will review all documentation. The PI will determine the balance between risks and benefits and will notify the IRB if a change in the intervention protocol in order to minimize risk is required. In the case of an actual adverse event, the PI will complete the "IRB Report of an Internal Adverse Event" form and report the event to the IRB within 5 days of the event.

8.2 Dosage change based on toxicity.

Not applicable. No modification of medication will be included.

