1.0 BACKGROUND AND HYPOTHESES

Although Parkinson's disease (PD) has been mainly viewed as a movement disorder, the pathophysiology of declined motor function incorporates impairments of multiple systems (sensory, motor, and cognition). Specifically, it has been demonstrated that cognitive function may play an essential role in daily motor function for individuals with PD^{1,2}. Cognitive dysfunction involving set-shifting and attentional control has been found to be associated with movement slowness in performing a finger sequence task and freezing of gait^{3–8}. The above results are in line with the clinical observations that motor performance in individuals with PD is degraded when the cognitive load of motor tasks increases, such as talking on the phone while walking or maneuvering between people in a crowded mall. Furthermore, a recent rodent model indicates that cognitive dysfunction may occur prior to the onset of motor symptoms⁸. Human studies also show that 25-30% of individuals with PD exhibit cognitive impairments at the time of diagnosis ^{9,10}. The overall evidence suggests that cognitive dysfunction may contribute to degraded motor function.

Interestingly, emerging evidence demonstrate that aerobic exercise and resistance training can improve cognitive function in individuals with PD^{11–15}. One study done by Ridgel et al. (2009) shows enhanced cognitive function after 30-min passive cyclying¹². The findings indicate that there is a tight interplay between motor and cognitive function in individuals with PD. Therefore, targeting cognitive function and incorporating cognitive training into physical rehabilitation may be important as it may better help individuals with PD to transfer the learned skill into real-world daily activities. Although there is mounting evidence for the benefits of physical exercise in PD, few studies investigate whether combining cognitive training with physical exercise can provide additional benefits than physical exercise alone.

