9.0 CLINICAL AND LABORATORY EVALUATIONS AND STUDY CALENDAR

Evaluation	1 st Pre-training assessment	1 st Post-training assessment		2 nd Pre-training assessment	2 nd Post-training assessment
Demographics form	Х				
Montreal Cognitive Assessment (MoCA)	X				
Activities-specific Balance Confidence Scale (ABC)	X				
History of Falls Questionnaire	Х		N		
Physical Activity Questionnaire	Х		2-m		
Geriatric Depression Scale (GDS)	Х		on		
Modified Physical Performance test (mPPT)	Х	Х	th wa	Х	Х
Movement Disorder Society- sponsored revision of the Unified Parkinson's Disease Rating Scale (MDS-UPDRS)	Х	Х	2-month washout period	Х	Х
Self-Efficacy for Exercise Scale (SEES)	Х	Х	d	Х	Х
Trail-making test (TMT)	Х	Х		Х	Х
Parkinson's Disease-Cognitive Rating Scale (PD-CRS)	X	Х		Х	Х
Quotient system test	X	Х		Х	Х
Functional MRI	Х	Х		Х	Х
Quantatitive EEG	Х	Х		Х	Х
α-synuclein and DJ-1	Х	Х		Х	Х

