3	Perform task big enough that able to complete task in one attempt – 14 inch height chair	Complete 40+ repetitions		nity support with pelvis or feet surface (i.e., dynadisk; airex)		Maintain end upright posture – no wobbling, no toes up end position	Working memory loading (e.g., counting backwards, adding numbers)
Pair 1:	Multi-plane Locomotor Tasks:	Turns, Stepping		and between obstacles, steps or	stairs, (see obsta	cle course layout for t	his activity)
Level	Amplitude/speed	Endurance	Balance		Vision	Accuracy	Cognition
1	Largest step at comfortable speed	15 minutes with unlimited # of rest breaks	PT UE support	Stable surface but obstructed path with obstacles to walk around and over (short objects)	1	Not knocking over any obstacles	Simple reaction time task
2	Maintain largest step length and increase speed	15 minutes with 1 -2 rest breaks allowed	Cane	Stable with obstacles to walk around and over (tall objects) and Unstable surfaces (thick floor mat)	0	Predictable start and stops and 90° turns	Choice reaction time task
3	Maintain largest step length and as fast as possible safely	15 minutes with no rest breaks	No Support	Stable with obstacles to walk around and over (tall objects and Unstable surfaces (step on airex pads or river stones)	with head turns	Unpredictable start and stops and turns of 90° (2-steps), 180° (max of 4 steps), or 360° (max of 8 steps)	Working memory loading (e.g., counting backwards, adding numbers)

Pair 2: G	ait					
Level	Amplitude/speed	Endurance	Balance	Vision	Accuracy	Cognition
1	Largest step at comfortable speed	15 minutes with greatest number of rest breaks	Forward, side-ways and backward walking with PT in front giving UE support	No manipulation	No accuracy manipulation	Simple reaction time task
2	Maintain largest step length and increase speed	15 minutes with 1 -2 rest breaks allowed	Forward, side-ways and backward walking with a cane	Sunglasses or no-body glasses	PT directed stop and start	Choice reaction time task
3	Maintain largest step length and as fast as possible safely	15 minutes with no rest breaks	Forward, side-ways and backward walking with no UE support	Sunglasses or no-body glasses canning environment with head turns	Stop and start and regular turns (left, right, 180° or reversal from forward to back or side stepping direction	Working memory loading (e.g., counting backwards, adding numbers)
Pair 2: R	each & Grasp	-		-		-
Level	Amplitude/speed	Endurance	Balance	Vision	Accuracy	Cognition

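### Falls are not a named exercise risk or a session-record item and are asked about only at baseline, so uninjured falls and near-falls are not systematically captured by training

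*Combined protocol and SAP*

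**What the plan says.** **Risks.** Section 8.1 describes the risks of training twice. Its opening paragraph names the time commitment and "the potential for muscle soreness, strains, or sprains that is a natural part of participating in a training program". Its paragraph on exercise adds: "These risks include muscle strains and/or sprains and muscle soreness, in addition to cardiovascular events such as heart attack and stroke". Neither mentions falls.

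**Session record.** Later in Section 8.1, the therapist's documentation at each session "will monitor 1) the subjects cardiovascular exercise tolerance through vital sign assessment and 2) any signs of musculoskeletal adverse response". Escalation has a threshold: "The PT will be instructed to contact the PI immediately if an adverse response that requires medical intervention occurs".

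**General reporting.** Section 8.3 begins: "All adverse events will be reported to the IRB on the USC Health Sciences Campus". It sets a 24-hour report for unexpected, severe or fatal events, and a summary in the annual review and final report for minor ones.

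**Instruments and analysis.** In the Section 9.0 calendar, the "History of Falls Questionnaire" is marked only at the first pre-training assessment, as is the balance-confidence scale. No outcome in Section 3.2 is a fall measure. Section 13.0 covers motor, cognitive, connectivity and biomarker outcomes and plans no safety summary.

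**Difference between trainings.** Both trainings use the same six functional tasks. Section 3.1 gives SMARTfit one further component, cognition. Section 1.0 states that "motor performance in individuals with PD is degraded when the cognitive load of motor tasks increases". At level 3 of the multi-plane locomotor task, Appendix 1 includes "Unstable surfaces (step on airex pads or river stones" with no support. Level 3 of floor transfers and of single-limb standing has the eyes closed.

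**The concern.** The protocol's own rationale raises a safety question specific to the comparison. If added cognitive load degrades movement in this population, and SMARTfit adds that load to tasks that challenge balance, then loss of balance is a harm that could plausibly differ between the two trainings. The plan has no prompt that would show whether it does.

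The pilot is meant to inform a larger study. As written, it could report motor and cognitive changes for each training with no defined count of falls or near-falls beside them. Unprompted events of this kind cannot be reliably recovered afterwards, because a caught stumble that nobody wrote down leaves no trace.

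**Working it through.** The plan gives no figure on falls, so there is nothing to reproduce. The check has two parts.

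**1. Where would a fall be recorded?**

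| Event | Session record (8.1) | Escalation to the PI (8.1) | Adverse event route (8.3) | Falls questionnaire (9.0) |
|---|---|---|---|---|
| Fall with injury, in session | Yes, as a musculoskeletal response | If medical intervention is needed | Yes | No, baseline only |
| Fall without injury, in session | Fits neither stated item | Not required | Only if someone classes it as an adverse event | No |
| Near-fall caught by the therapist | Fits neither stated item | Not required | Unlikely without a definition | No |
| Fall at home during training or washout | Not a session event | By the participant's own call to the PI | Only if reported | No |

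Because falls are not named, it is also unclear whether a harmless fall would count as unexpected (24-hour report) or minor (annual summary). Nothing in Section 8.3 or 13.0 splits adverse events by training or period.

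**2. What could recorded falls show?**

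Inputs: 24 sessions per training (Section 3.1); 10 expected completers and 12 recruited (Section 13.0).

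- Sessions per training: 10 × 24 = 240, or 12 × 24 = 288.
- One-sided 95% upper bound on the risk per participant after zero fallers, 1 − 0.05^(1/n): n = 10 gives 25.9%; n = 12 gives 22.1%.
- The same bound per session, assuming independent sessions: 1 − 0.05^(1/240) = 1.24%; 1 − 0.05^(1/288) = 1.03%. Sessions cluster within 10 to 12 people, so independence is doubtful and the participant bound is the safer one to quote.
- Chance of at least one faller in one training, 1 − (1 − p)^n. The documents give no fall rates, so p is assumed. At p = 10%: 65% (n = 10) to 72% (n = 12). At p = 20%: 89% to 93%.
- Formal comparison by an exact two-sided McNemar test: with all discordant participants in one direction, p = 2 × 0.5^k. k = 5 gives 0.063 and k = 6 gives 0.031, so at least six are needed for p < 0.05.
- Power of that test under assumed faller risks, independent within participant: 30% versus 10% gives 2% (n = 10) to 4% (n = 12); 50% versus 10% gives 19% to 32%.

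Recorded falls would therefore give a useful description, and would probably show at least one faller if the risk is 10% or more. They would not support a test.

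**The case against.** The best defence is that the plan is not silent on harm. All adverse events go to the IRB, participants are told they can call the PI, and the PI reviews all documentation monthly. An injurious fall has a route, and many would also be noted as a musculoskeletal response. A reader might infer that falls go entirely unmeasured; Section 8.3 does not support that. This part of the defence stands.

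A reader might also infer that falls are the harm most likely to differ between the trainings. The documents give no fall rates and do not rank harms. Section 1.0 speaks of degraded motor performance, not of falls under supervision. Eligibility is limited to Hoehn and Yahr stage 1–2 with independent ambulation, staffing is 1:1, and each component is scaled to the participant. The most demanding conditions are level 3 entries, while level 1 of most tasks allows hand, chair or therapist support. The supportable claim is that falls are a plausible difference. These safeguards may lower the number of falls, but they do not record them.

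It can also be said that the therapist sees instability directly, and that several Appendix 1 accuracy criteria concern it. That is fair: nothing in the protocol makes progression depend on a fall count, so the gap lies in reporting.

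Falls at home are a weaker part of the case. The mechanism concerns load during the tasks, and washout falls are hard to attribute to either training. They are worth asking about for context.

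Finally, the session form itself is not shown and the consent pages were removed. The point is limited to the protocol text and says nothing about what consent discloses.

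**Conclusion.** The concern holds in a limited form. In the protocol text, falls are not a named exercise risk, are not an item in the therapist's session record, and are asked about at one of four assessments. Injurious falls should surface through general reporting. Uninjured falls and near-falls are not systematically captured, and no adverse event is set out by training, although the distinguishing feature of SMARTfit is a load that the protocol says degrades movement.

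This is a worthwhile low-cost improvement. It does not affect the efficacy analysis, and it is not evidence that either training is unsafe. The gain is modest: the bound after zero fallers is wide, and it assumes that the 10 to 12 participants complete the training concerned. Nobody should expect the pilot to establish whether SMARTfit causes more falls.

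**What to change.** 1. Name falls in the Section 8.1 risk list.
2. Add a third item to the therapist's session record: falls and near-falls, with task, difficulty level, training and period. Define a near-fall as loss of balance needing unplanned therapist contact, because planned support is part of some level 1 tasks.
3. Repeat the existing falls questionnaire at the three later assessments, with recall since the previous visit.
4. State in Section 13.0 that falls, near-falls and other adverse events will be reported descriptively by training, giving numbers of events and of participants affected, with session and participant denominators and no hypothesis test.

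The cost is a line on an existing form and a few minutes at three visits already scheduled. No extra staff are needed, because the therapist is already present 1:1, and no training or stopping rule changes.
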